Clinical Study Protocol

Protocol Title: **A Phase 2b Open-Label Single Arm Study to Evaluate the Efficacy and Safety of Oral HBI-8000 in Patients with Relapsed or Refractory Peripheral T-cell Lymphoma (PTCL)**

Protocol Number: **HBI-8000-203**

NCT Number: **NCT02953652**

Version: **6.0**

Date of Protocol: **19 July 2021**

Sponsor: **HUYABIO International, LLC**

HBI-8000-203 Protocol Synopsis

Name of Sponsor/Company:	HUYABIO International, LLC	
Study Drug:	HBI-8000	
Title of Study:	A Phase 2b Open-Label Single Arm Study to Evaluate the Efficacy and Safety of Oral HBI-8000 in Patients with Relapsed or Refractory Peripheral T-cell Lymphoma (PTCL)	
Protocol No:	HBI-8000-203	
Study site(s):	25 to 35 sites in Japan and 10 to 15 sites in South Korea	
Study duration:	Approximately 66 months	Phase: 2b
Planned study period:	4Q 2016 (first patient in) to 3Q 2018 (last patient in) 2Q 2022 study completion	
Objectives:		
Primary:	
 To determine the efficacy of HBI-8000 administered twice a week (BIW) continuously 	
Secondary:	
 To evaluate the safety and tolerability of HBI-8000 administered BIW continuously 	
Endpoints:		
Primary:	
 Objective response rate (ORR; Complete Response [CR] + Partial Response [PR]) 	
Secondary:	
 ORR by disease subtype (see inclusion criteria) Median duration of progression-free survival (PFS) Median duration of response (DOR) Safety 	
Exploratory:	
 Median duration of overall survival (OS) Pharmacokinetics (selected sites) 	
Study Design:	
This is a Phase 2b, open-label, non-randomized, single arm study to evaluate the safety, efficacy, and PK of HBI-8000 40 mg BIW in patients with relapsed or refractory PTCL (R/R PTCL). HBI-8000 will be administered orally approximately 30 minutes after any regular meal. The treatment will be continuous, with 3-4 days between dosing. A cycle is defined as 28 days solely for the purpose to schedule assessments required by the study.
 
The study will continue till the last active Japanese subject initiates administration of the commercial product of HBI-8000 after the marketing authorization approval for relapsed or refractory PTCL in Japan. If there is no subject who is receiving study treatment at the time of the PTCL approval in Japan, the whole study will be completed at the time of the approval.
 
In Japan, “Phase 2 study” shall be read as “post-marketing clinical study” and “investigator” shall be read as “post-marketing clinical study investigator” in this protocol after the marketing approval. In addition, other related terms are to be replaced in accordance with Article 56 of the Ministerial Ordinance on the Standards for the Implementation of Clinical Studies on Pharmaceutical Product (Japan GCP).
 
Treatment-related adverse events (AEs) will be graded according to National Cancer Institute Common Terminology Criteria for Adverse Events (NCI CTCAE) version 4.03. In the event of unacceptable toxicities, study drug will be held until recovery and dosing will be resumed at reduced dose level, following protocol guidelines. An unacceptable toxicity is defined as the following:
	

- Grade 4 afebrile neutropenia > 7 days despite optimal growth factor support
- Grade ≥ 3 febrile neutropenia or neutropenic infection
- Grade ≥ 3 thrombocytopenia with clinically significant bleeding or Grade ≥ 3 thrombocytopenia requiring a platelet transfusion
- Grade ≥ 3 nausea, vomiting, diarrhea, or electrolyte imbalances lasting greater than 48 hours despite optimal prophylactic and curative treatment
- Grade ≥ 3 allergic reaction
- Grade ≥ 3 other non-hematologic AEs
- Treatment delay >14 days secondary to recovery from study drugs- related AEs

For determination of efficacy, HBI-8000 administration will be continued until disease progression (PD) or unacceptable toxicities are observed despite appropriate dose reduction or treatment interruption. Study drug treatment will be discontinued after the PTCL approval when the commercial product of HBI-8000 is available at the study sites.

Number of patients:	40 patients evaluable for efficacy with approximately 27 from Japan and 13 from Korea. To ensure meeting this target, an estimated 50 to 60 patients would be enrolled in anticipation that some patients may not complete study treatment.
Entry Criteria:	
Inclusion
 
 1. Histological or cytological diagnosis of the following peripheral T-cell lymphoma (PTCL) subtypes as defined by the WHO classification (2008) may be included: 
 a. PTCL, NOS b. Angioimmunoblastic T-cell lymphoma (AITL) c. Anaplastic large-cell lymphoma (ALCL), ALK$^+$ d. Anaplastic large-cell lymphoma (ALCL), ALK$^-$ e. Enteropathy-associated T-cell lymphoma (EATL) f. Hepatosplenic T-cell lymphoma g. Subcutaneous panniculitis-like T-cell lymphoma 2. Patients for whom at least 1 measurable lesion is confirmed by the lesion assessment at baseline; An evaluable lesion is defined according to Cheson criteria 2014. 3. Relapsed or refractory disease after receiving ≥ 1 prior systemic therapy with anti-tumor agent(s) and there is no other standard treatment which can be considered appropriate for patients. Systemic therapy is defined as frontline chemotherapy or immunotherapy administered systemically. 4. Male or female, age 20 years or older 5. Eastern Cooperative Oncology Group (ECOG) Performance Status of 0 to 2 6. Life expectancy of greater than 3 months 7. Meeting the following baseline laboratory criteria for screening: 
 a. Absolute Neutrophil Count $>1500/\mu\text{L}$ independent of growth factor support within 7 days b. Platelets $>75,000/\mu\text{L}$ independent of transfusion within 14 days c. Hemoglobin $>8 \text{ g/dL}$ independent of transfusion within 14 days d. Serum creatinine $< 1.5 \times \text{ULN}$ e. Serum aspartate aminotransferase/glutamyl oxaloacetic transaminase (AST/SGOT) and alanine aminotransferase/glutamyl pyruvic transaminase (ALT/SGPT) $\leq 3 \times \text{ULN}$

f. Serum Bilirubin $\leq 1.5 \times$ ULN

8. Negative serum pregnancy test for females of childbearing (reproductive) potential. Female patients of child bearing potential must use an effective method of birth control (e.g., hormonal contraceptive, intrauterine device, diaphragm with spermicide or condom with spermicide) during treatment period and 1 month thereafter. Males must use an effective method of birth control (2 barrier methods) during treatment period and 3 months thereafter.

Note: Female patients will be considered to be women of childbearing potential unless having undergone permanent contraception or postmenopausal. Postmenopausal is defined as at least 12 months without menses with no other medical reasons (e.g., chemical menopause because of treatment with anti-malignant tumor agents)

9. Signed informed consent

Exclusion

1. Patients in whom central nervous system lymphoma is recognized during screening (if suspected clinically, imaging study should be performed to confirm)
2. Male patients with QTcF >450 msec at screening, female patients with QTcF >470 msec at screening or patients with congenital long QT syndrome, clinically significant arrhythmia, history of congestive heart failure (New York Heart Association Class III or IV) or acute myocardial infarction within 6 months of starting the study drug
3. Patients with known hypersensitivity to benzamide class of compounds or any of the components of HBI-8000 tablets, and patients with prior exposure of HBI-8000
4. Patients with a history of second malignancy other than disease under study. The exceptions are diseases (excluding diseases listed below) that have been treated with curative intent with no evidence of recurrence in past 5 years. Furthermore, if the second malignancy is one of the following diseases that were treated with curative intent, it is only required that there is no evidence of recurrence in past 2 year.
 - a. Basal cell carcinoma of the skin
 - b. Squamous cell carcinoma of the skin
 - c. Cervical carcinoma in situ
 - d. Carcinoma in situ of the breast
 - e. An incidental histological finding of prostate carcinoma (TNM stage T1a or T1b)
 - f. Early-stage gastric cancer treated with endoscopic mucosal resection or endoscopic submucosal dissection
 - g. Thyroid cancer with differentiated histology (e.g. papillary) treated with curative intent
5. Autologous stem cell transplantation within 12 weeks (84 days) of starting the study drug
6. History of allogeneic stem cell transplantation
7. Organ transplantation recipients except for autologous hematopoietic stem cell transplantation
8. Uncontrolled inter-current infection
9. Hepatitis B surface antigen-positive, or hepatitis C virus antibody positive. In case hepatitis B core antibody and/or hepatitis B surface antibody is positive even if hepatitis B surface antigen-negative, a

	
hepatitis B virus DNA test (real-time polymerase chain reaction (PCR) measurement) should be performed and if positive, the patient should be excluded from study
 
 10. Any history of testing positive for human immunodeficiency virus (HIV) or known acquired immunodeficiency syndrome (AIDS) 11. Uncontrolled diabetes mellitus, hypertension, endocrine disorder, bleeding disorder 12. Major surgery or radiation therapy within 28 days of starting the study drug 13. Receiving investigational agents or anti-cancer therapy, within 28 days, nitrosourea or mitomycin C within 42 days of starting the study drug 14. Receiving antibody therapy for PTCL within 12 weeks of starting the study drug 15. Women who are breastfeeding or women who are not willing to stop breastfeeding during study treatment period and for 30 days after the last dose of study drug 16. Potential for non-compliance or at increased risk based on investigator's judgement
Excluded Prior or Concomitant Medications or Therapy:	
The following drugs are prohibited.
 
 • Drugs known to produce significant QT prolongation and ventricular dysrhythmias (see Section 9.6) Prohibited from signing informed consent through the EoT assessment • Anti-cancer therapy other than study medication Prohibited during the study and within the following time intervals prior to the first dose of study drug. 
 - 4 weeks for anti-cancer chemotherapy - 6 weeks for nitrosourea and mitomycin C - 12 weeks for anti-cancer monoclonal antibody therapy 
Corticosteroid prescribed for medical conditions other than lymphoma is not considered as an anti-cancer therapy for this study, for example: chronic obstructive pulmonary disease, allergy, topical steroids for rash.

Treatments:	
Study drug is to be taken after any regular meal twice weekly, each dose separated by 3-4 days. Treatment will continue until PD in the absence of unacceptable toxicity, whichever is earlier. Study drug treatment will be completed when the commercial product of HBI-8000 is available at the study sites after the PTCL approval.

Efficacy Data:	
Response and progression for PTCL will be evaluated according to the revised criteria for response assessment in lymphoma [Cheson 2014]. To be included in final efficacy analyses, the histopathology diagnosis of disease will be verified by Central Pathology Review, and disease response will be confirmed by Independent Radiology and Independent Overall Efficacy Review.

Safety Data:	
All patients who receive at least one dose of HBI-8000 will be evaluable for safety. Adverse event severity (grade) will be defined according to Common Terminology Criteria for Adverse Events (CTCAE) Version 4.03. Serial ECGs and clinical laboratory tests will be collected to evaluate safety and potential toxicity. Laboratory and other tests, as appropriate to the clinical situation, may be obtained more frequently than stipulated in the schedules of events.
 
All reported AEs will be collected, evaluated and coded using Medical Dictionary for Regulatory Activities (MedDRA).

Pharmacokinetics data from selected sites:	At sites participating in population PK assessments, blood samples for plasma HBI-8000 measurement will be taken on Day 1 of Cycle 1 at pre-dose, 1 h (\pm 15 min), 2 h (\pm 15 min), 3 h (\pm 15 min), 4 h (\pm 15 min), 5 h (\pm 30 min), 7 h (\pm 30 min), 24 \pm 1 h, 48 \pm 1 h and 72 \pm 1 h. On Day 1 of Cycle 2 (e.g., C2D1) PK samples will be taken at pre-dose and 1 h (\pm 15 min), 2 h (\pm 15 min), 3 h (\pm 15 min), and 4 h (\pm 15 min). On Day 1 of Cycles 3 to 6, only pre-dose PK samples will be taken.
Statistical Procedures:	
Statistical analysis for all safety, efficacy, and PK parameters will be primarily descriptive in nature. Categorical variables will be summarized by frequency distributions (number and percentages of patients), continuous variables will be summarized by mean, standard deviation, median, minimum, maximum, and time-to-event variables will be summarized using Kaplan-Meier methods and figures for the estimated median time. A formal statistical analysis plan will be completed prior to database lock and any study-related analyses.	
Disease diagnosis including histological subtypes will be confirmed by central pathology review conducted by independent pathologists.	
Efficacy should be analyzed using Full analysis set (FAS) and Per protocol set (PPS). The FAS is defined as Patients meeting all eligibility criteria and having received at least one dose of study medication, and at least one efficacy assessment of disease with either imaging studies or clinical examination after receiving study medication.	
The PPS is defined as Patients meeting all eligibility criteria and having completed Cycle 1 treatment or discontinued study treatment during cycle 1 due to clinical PD. It should be noted that the PPS includes subjects who discontinue within Cycle 1 due to clinical PD without imaging studies to assess disease status.	
In addition, Patients who are assessed as Non-PTCL by the central pathology review committee should be excluded from the FAS and PPS for efficacy. The non-PTCL subjects will be included in safety analysis for the study.	
The primary efficacy analysis is conducted in the PPS. The Efficacy analysis using the FAS will be also reported.	
It is estimated that 40 evaluable patients are adequate to provide efficacy assessment. Assuming a 30% ORR in this population of 40 evaluable patients, the conclusion would be that there is a 95% chance that the ORR in this protocol population would lie between 15.8% and 44.2%. The power for showing the response rate $>10\%$ at 5% two-sided alpha in 40 patients is 89%.	
All patients who have received any amount of study medication will be considered as evaluable for safety. Safety data will be summarized with descriptive statistics and frequency tables and will include AEs, hematology, coagulation, serum chemistry, urinalysis, vital signs, and ECG data. Laboratory values will be summarized by numerical value and toxicity grade.	

TABLE OF CONTENTS

SIGNATURES.....	2
HBI-8000-203 PROTOCOL SYNOPSIS	3
LIST OF ABBREVIATIONS AND DEFINITIONS OF TERMS	13
1.0 INTRODUCTION.....	15
1.1 Background Information	15
1.2 Histone Deacetylase as a Therapeutic Target in Cancer... 	15
1.3 Rationale for the Use of HBI-8000 for the Treatment of Cancer	16
1.3.1 Immunomodulatory Mechanisms Integrate with Cancer Cell Intrinsic Mechanisms of Cell Killing by HDACi.....	17
1.4 Nonclinical Studies.....	18
1.5 Clinical Pharmacology.....	19
1.5.1 Absorption	19
1.5.2 Distribution.....	20
1.5.3 Metabolism and Excretion.....	20
1.6 Clinical Studies.....	20

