2.6 Study Procedures Overview

Patients may be treated in this study as long as they receive clinical benefit (stable disease or a response) in the absence of unacceptable toxicity. Disease progression would be determined by investigators based on local radiology findings and clinical judgement. No independent radiology review is required prior to designation of PD and treatment discontinuation. Independent Radiology Review and Independent Overall Efficacy Review will be performed for final efficacy analyses at the completion of this study.

To ensure patient safety, a data safety monitoring board (DSMB) will convene to review the cumulative safety profiles of study patients at following milestones: first 6 patients completing at least 1 cycle, 12, 18, 30 patients have been treated for at least 1 cycle and at end of treatment Phase of the study. Based on the observed safety, dose and regimen of ongoing treatment may be modified as needed. For all patients, weekly safety laboratory tests will be obtained during the first 28 days and closely monitored for safety signals, especially for neutropenia and transaminase elevation.

It is estimated that each patient will be on study for up to 42 months after enrollment. Assuming that 24 months are needed to meet accrual target, the study period would be of 66 months to allow efficacy and safety determination. After study drug is discontinued, patients will be followed as described in Sections 2.6.4 and 2.6.5.

Patients will be screened by the study site investigator prior to entry into the study. Patients will receive a detailed explanation of the study design, and the potential risk/benefit of treatment will be disclosed to patients prior to the screening process. Only eligible and consenting patients will be enrolled into the study. Local histopathology report could be used to consent patient. Central pathology review will be completed before efficacy analysis. The investigator will maintain a pre-screening log to record all patients prior to screening.

Similarly, local radiology reports on disease status will guide investigator's decision on study treatment, including discontinuation. At end of the study, tumor response of each patient will be reviewed by independent radiologists and oncologists in a blinded fashion to obtain best response, dates of response and progression. The data from independent and local assessment will be analyzed in parallel in final study report.

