2.6.1 Screening Assessments (within 28 days prior to start of treatment)

Written informed consent for participation in the study must be obtained before performing any study-specific screening tests or evaluations. Informed Consent Forms (ICFs) for all patients screened (whether enrolled or not) will be maintained at the study site.

All screening and baseline assessments must be completed and reviewed to confirm that patients meet all eligibility criteria. An Eligibility Screening Form (ESF) documenting the investigator's assessment of each screened patient with regard to the protocol's inclusion and exclusion criteria is to be completed and kept at the study site.

Screening assessments include medical history and concomitant medications, documentation of PTCL diagnosis in accordance with the WHO revised classification (WHO 2008) and treatment history. To consent a patient to allow screening procedure, local histology diagnosis for PTCL is acceptable. Unstained tumor pathology slides will be sent to pathology central laboratory and stained at the central laboratory. The images will be captured from the slides for central pathology review that is to be completed before efficacy analysis. For patients who do not have enough tumor tissue archived, a new biopsy will be requested. However, insufficient tumor tissue in archive or inability to perform new biopsy for any reason does not

exclude patients from entering this study. Reasonable efforts should be made to support central pathology review.

Screening assessments will be performed within 28 days prior to Cycle 1 Day 1 (C1D1). A pretreatment bone marrow test (aspiration or biopsy) would be required. Results of standard-of-care tests or examinations performed prior to obtaining informed consent and within 28 days prior to C1D1 may be used (and do not need to be repeated for screening unless they do not meet the criteria defined in the protocol). Similarly, tumor assessment tests <2 weeks outside the 28-day window in the absence of clinical evidence of PD, the results may be accepted.

Women of childbearing potential must agree to practice effective contraceptive measures after signing informed consent. A negative serum pregnancy test will be obtained during screening.

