5.0 STATISTICS

5.1 General Statistical Considerations

Protocol HBI-8000-203 is an open-label, Phase 2b pivotal study evaluating HBI-8000 for regulatory approval in Japan and South Korea for the indication of relapsed or refractory PTCL. The main analysis will be conducted for the purpose of regulatory submission of this product. The data cut-off (DCO) for the main analysis is set at the time when the last patient completes at least one post-efficacy assessment. The eCRF data by the DCO needs to be cleaned to have no unresolved queries. All independent reviews (including the Central Pathology Review, the independent radiological review, the Independent Overall Efficacy Review and review by the Data Safety Monitoring Board) by the DCO need to be completed before the main analysis. The data after the main analysis will be provided at the end of the study as a supportive material.

Statistical analysis for all safety, efficacy, and PK parameters will be primarily descriptive in nature. Categorical variables will be summarized by frequency distributions (number and percentages of patients), continuous variables will be summarized by mean, standard deviation, median, minimum, maximum, and time-to-event variables will be summarized using Kaplan-Meier methods and figures for the estimated median time.

All analyses, summaries, and listings will be performed using SAS software (version 9.3 or higher)

A detailed methodology for summary and statistical analysis of the data collected in this trial will be documented in a Statistical Analysis Plan (SAP) that will be dated and maintained by HUYABIO. The SAP may modify the plans outlined in the protocol; however, any major modifications of the primary endpoint definition and/or its analysis will also be reflected in a protocol amendment.

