5.5.2 Efficacy Population

Efficacy should be analyzed using FAS and PPS.

The FAS is defined as Patients meeting all eligibility criteria and having received at least one dose of study medication, and at least one efficacy assessment of disease with either imaging studies or clinical examination after receiving study medication.

The PPS is defined as Patients meeting all eligibility criteria and having completed Cycle 1 treatment or discontinued study treatment during cycle 1 due to clinical PD. It should be noted that the PPS includes subjects who discontinue within Cycle 1 due to clinical PD without imaging studies to assess disease status.

In addition, Patients who are assessed as Non-PTCL by the central pathology review committee should be excluded from the FAS and PPS for efficacy. The non-PTCL subjects will be included in safety analysis for the study.

The primary efficacy analysis is conducted in the PPS. The Efficacy analysis using the FAS will be also reported.

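### Does the Synopsis sentence on central pathology review remove patients with no central result from the primary response-rate analysis?

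*Combined protocol and SAP*

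**What the plan says.** The Synopsis, under Efficacy Data, says "To be included in final efficacy analyses, the histopathology diagnosis of disease will be verified by Central Pathology Review", and continues "and disease response will be confirmed by Independent Radiology and Independent Overall Efficacy Review".

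The analysis sets are defined under Statistical Procedures in the same Synopsis and again in Section 5.5.2. The FAS requires eligibility, at least one dose and at least one post-dose efficacy assessment. The PPS requires eligibility and either completion of Cycle 1 or discontinuation in Cycle 1 for clinical progression. Both places add one pathology rule: "Patients who are assessed as Non-PTCL by the central pathology review committee should be excluded from the FAS and PPS for efficacy". Both make the PPS the primary efficacy set and have the FAS reported as well.

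The local diagnosis is enough for entry (Sections 2.6 and 2.6.1). A new biopsy is requested when archived tissue is short, but "insufficient tumor tissue in archive or inability to perform new biopsy for any reason does not" bar the patient from the study. On timing, Section 2.6 says "Central pathology review will be completed before efficacy analysis", and Section 5.1 wants all independent reviews finished before the main analysis, whose cut-off "is set at the time when the last patient completes at least one post-efficacy assessment". Section 5.9 takes the subtype for the subtype ORR from central review.

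**The concern.** The opening words of the Synopsis sentence sound like a condition on patients. A patient with neither adequate archived tissue nor a new biopsy has an unverified diagnosis and would then leave the final efficacy analyses. Under the set definitions the same patient stays, because a patient who was never assessed has not been assessed as non-PTCL. Both texts stand in version 6.0, and neither mentions a missing central result.

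At stake is the denominator, and possibly the numerator, of the primary ORR in a study that Section 5.1 calls pivotal for approval in two countries. If the choice were made after responses were known, it could be made to suit the result.

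**Working it through.** **The plan's own figure.** Inputs from Section 5.2: 40 evaluable patients, target ORR 30%, benchmark 10%, 5% two-sided alpha, power 89%.

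- Critical count: the smallest r with P(X ≥ r | 40, 0.10) ≤ 0.025. This is r = 9, with tail probability 1.55%.
- The exact lower 95% limit is 10.84% for 9/40 and 9.05% for 8/40, so r = 9 is also the smallest count whose exact interval lies above 10%.
- Power: P(X ≥ 9 | 40, 0.30) = 88.9%. The stated 89% reproduces.

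**The texts side by side.**

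1. The grammatical subject of the Synopsis sentence is the diagnosis, not the patient. It stands under Efficacy Data, among statements of how response is assessed, and it matches the purely procedural sentences in Section 2.6 and under Statistical Procedures.
2. Section 5.5.2 is the section on the efficacy population. It defines the sets, names the primary one, and gives a single pathology exclusion, a positive central finding of non-PTCL. An otherwise eligible patient with no finding meets the definition.
3. The version 4.0 table of changes records the present set definitions as a clarification. The pathology clause in the Synopsis already stood in earlier text. The definitions are therefore both later and more specific.
4. The second half of the sentence does not settle the matter. Section 5.5.2 notes that "the PPS includes subjects who discontinue within Cycle 1 due to clinical PD without imaging studies to assess disease status". Sections 3.5.4 and 5.9 let independent oncologists work from clinical data, so such a patient can still be confirmed. I give that half no weight either way.

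**Size.** The documents do not say how many patients lack a central result, so k = 1 to 4 is assumed. Calling a trial positive when the exact lower limit exceeds 10% is also an assumption, borrowed from the power statement.

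| n | critical count | type I error at 10% | power at 30% |
|---|---|---|---|
| 36 | 8 | 2.35% | 88.8% |
| 37 | 9 | 0.93% | 82.4% |
| 38 | 9 | 1.11% | 84.8% |
| 39 | 9 | 1.31% | 87.0% |
| 40 | 9 | 1.55% | 88.9% |
| 41 | 9 | 1.81% | 90.6% |
| 42 | 9 | 2.11% | 92.0% |
| 43 | 9 | 2.44% | 93.3% |
| 44 | 10 | 1.03% | 89.1% |

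The dip at 37 comes from the discreteness of the binomial.

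- *40 verified patients plus k unreviewed.* Power is 88.9% if the k are left out and 90.6%, 92.0%, 93.3% or 89.1% if they are kept.
- *40 patients of whom k are unreviewed.* Power is 88.9% if they are kept and 87.0%, 84.8%, 82.4% or 88.8% if they are left out.

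The chance that the two readings disagree is the sum, over a ~ Binomial(verified, 0.3) and b ~ Binomial(k, 0.3), of the probability that exactly one of a and a + b reaches its critical count. This takes reviewability as unrelated to response. It gives 1.7%, 3.1%, 4.4% and 4.3% in the first case and 1.9%, 4.1%, 6.5% and 4.5% in the second.

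**The case for a change.** The best argument for a change is that Section 5.5.2 keeps unreviewed patients only by silence. The Synopsis sentence was edited for version 3.0 and has been carried forward since, and no separate SAP text is available here to settle the point. The reported estimate can also move more than the power figures suggest. With 12/40 responders (30.0%), leaving out four patients gives anything from 8/36 (22.2%) to 12/36 (33.3%), depending on how many of the four responded. At 8/36 the exact lower limit is still 10.1%. Leaving out six could give 6/34 (17.6%, lower limit 6.8%). Choosing the more favourable rule afterwards would raise type I error to at most 2.59% for k of 1 to 4. Unreviewed patients also have no central subtype for the subtype ORR.

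It stands that a missing central result is not addressed in words. The shifts in the estimate, however, need several patients with neither archived tissue nor a new biopsy, and the larger ones need nearly all of them to be responders. A sensitivity ORR, a review-status field and an unclassified subtype category would be good practice, but the primary analysis is sound without them. Rewording may also come too late: the Synopsis plans "4Q 2016 (first patient in) to 3Q 2018 (last patient in) 2Q 2022 study completion", version 6.0 is dated July 2021, and the cut-off for the main analysis needs only one efficacy assessment in the last patient.

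**Conclusion.** No change follows. The conflict arises only if a loosely built Synopsis sentence is read as a patient-level filter, against a dedicated section that defines the sets, names the primary one and states the only pathology exclusion. An analyst following Section 5.5.2 keeps otherwise eligible unreviewed patients on their local diagnosis, and that gives a sound primary analysis. The alternative reading would be sound too. Type I error is at most 2.44% under either, and if a filter were intended, the requirement of 40 evaluable patients from 50 to 60 enrolled would mean 40 verified patients and the planned 88.9% power.

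This rests on an assumed 1 to 4 unreviewed patients, on the 10% benchmark serving as a boundary that the plan does not set, and, for the disagreement rates, on reviewability being unrelated to response. The conclusion about who is analysed needs none of these, because it follows from the text of Section 5.5.2.
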